#### **21.4.3.1.5. Subjective Refraction**

Subjective refraction allows one to determine the best correction for a subject to perform the visual acuity tests. The “**push plus**” approach is used. Add minus diopter spherical corrections **only when the subject is able to read at least one more letter** on a line or a letter on a smaller line.

##### **21.4.3.1.5.1. Procedure**

1. Measure and record the distance vision of the eye being tested using Chart R while occluding the fellow eye. The fellow eye should be lightly patched with an eye pad or tissue and tape. Subjects should be reminded to blink and encouraged to use eccentric fixation, or their side vision, when necessary.
2. All refraction and vision testing must be done at 4 meters or 1 meter. Distance for 4 meters is 13 feet and 1.5 inches or 157.5 inches. The one meter distance is 39 and 3/8 inches.
3. All subjects should be seated for testing. A **rigid measuring device** should be used to measure the distance from the subject to the chart if testing is done at **1 meter**. The distance is measured from the outer canthus to the center of the second letter (left eye) or fourth letter (right eye) of the third line of the chart. For **4 meter** testing, **clear and permanent floor markings** should be used to mark the distance for consistency.
4. Place and adjust the trial frame on the subject's face so that the lens cells are parallel to the anterior plane of the orbits and centered in front of the pupils. Adjust the lens cells for the proper distance from the cornea. Be sure the trial frame is comfortable on the subject's face.
5. Occlude the left eye by lightly patching with the eye pad or tissue and tape.
  - a. Place the spherical lens correction in the compartment closest to the eye.
  - b. The cylindrical lens correction, if present, is placed in the compartment in front of the spherical correction. Adjust the axis.
6. **Spherical Correction:** To determine the highest plus or least minus sphere, refract the right eye. **The following refraction steps are recommended for visual acuities of**

**20/10 to 20/80 with the beginning approximate refraction. For visual acuities less than 20/80, refer to the refraction table for the appropriate sphere and cylinder powers and testing distance and follow a similar procedure.** Note: Whenever visual acuity is improved to a higher range, refraction should be performed with the smaller sphere and cylinder powers given for the better visual acuity level.

- a. Hold a **+0.50 sphere** in front of the subject's right eye. The subject should be looking at the smallest legible line on the visual acuity chart. In these exact words, ask the subject, **"Is this better, worse, or no change?"**
- b. If the subject responds that the vision is **worse or blurred**, remove the +0.50 sphere from in front of the trial frame and **go to Step 6d**.
- c. If the subject responds **better or no change**, remove the +0.50 sphere from in front of the trial frame and replace the spherical lens in the trial frame with a spherical lens that is one-half diopter more positive. Continue this procedure by returning to Step 6a and repeating this process **until a +0.50 makes the vision worse** or blurred and then go to Step 6d.
- d. Hold a **-0.50 sphere** in front of the subject's right eye. In these exact words, ask the subject, **"Is this better, worse, or no change?"** If the subject replies **"worse"** or **"no change,"** go to Step 6f. If they reply **"better"** go to step 6e.
- e. Hold the -0.50 sphere in front of the eye. If the subject responds that the vision is better, ask the subject to read the visual acuity chart. **Only when the visual acuity is improved, by at least one letter, may you increase the minus** by 0.50 (or decrease the plus) and repeat Step 6d. Whenever visual acuity is not improved, go to Step 6f.
- f. Remove the -0.50 sphere from in front of the eye and hold a +0.50 sphere in front of the right eye. In these exact words, ask the subject, **"Is this better, worse, or no change?"** If the subject responds that the vision is better or unchanged, then return to Step 6c. Otherwise, go to Step 7. **Spherical testing should always end with a plus lens.**

7. Cylinder Axis: To determine and refine the cylinder axis for **PLUS** cylinder, proceed as follows; (if **minus** cylinders are used, the appropriate technique using minus cylinders must be employed and minus cylinder must be used throughout the trial.)

- a. Have the subject look at a line which is either **one or two lines larger** than the smallest line the subject is able to read. Ask the subject to focus on a rounded letter such as, **"C"**, **"D"**, or **"O"**. The subject should focus on the same letter throughout this procedure.
- b. If a cylinder is present in the beginning approximate refraction, then go to Step 7c. Otherwise, follow the option listed below to determine if cylinder may be needed.

**Testing for cylinder when there is none in the beginning approximate refraction:**

Place a **+0.50 diopter** cylinder with a positive axis first at 90°, then compare this to no cylinder; repeat this procedure for 180°, then 45°, and 135° always

comparing to no cylinder after each axis position. If the subject says that the vision is improved at any one of the four axis positions, place a +0.50 cylindrical lens in the trial frame at the preferred axis and go to Step 7c. If the subject prefers no cylinder at all four axis positions, then go to Step 9.

- c. Place the +0.25 diopter hand held cross-cylinder (for VA 20/10 – 20/80) first with the positive axis 45° to the right of the preferred cylinder axis (as determined above), and second with the positive axis 45° to the left of the preferred cylinder axis. Ask the subject, “Which do you like better, position one or position two?” Also, tell the subject that both positions may blur their vision. The subject must choose the least blurred position, either one or two. “Neither” is allowed only if both positions are equally blurred or equally good.
- d. If “neither” position is better and this was the first test of axis position, move the axis of the cylinder in the trial frame 15° to the right or left and return to Step 7c. Otherwise, proceed to Step 7e.
- e. When one position is preferred over another, move the cylinder to the preferred positive axis position in the step sizes noted below and return to Step 7c. If no single position is better than another then go to Step 8.

Cylinder Refinement Cylinder Power	suggested axis step sizes Axis Step Sizes
<1.00D	15°
1.00 - <2.00D	10°
2.00 - <3.00D	5°
3.00 - <5.00D	3°
5.0 - <8.00D	2°

- 8. **Cylinder Power:** Cylinder power is refined by following the step:
  - a. Ask the subject to look at the **smallest line** that can be read on the visual acuity chart.
  - b. Test the cylinder power by placing 0.25 diopter cross-cylinder (for vision of 20/10 – 20/80) first with the positive axis and second with the negative axis coincident with the cylinder axis. Ask the subject, “Which is better, position one or position two?” Do not give the subject the choice of neither.
  - c. If the subject prefers the minus axis coincident with the cylinder axis, the total power of the correcting plus cylinder is reduced by 0.25 diopter. Repeat the process until the subject cannot choose one of the cross cylinder positions over the other. If the subject indicates a change that would introduce negative cylinder power, remove all cylinder power and continue testing for positive cylinder power at an axis 90° away from the previous axis. Otherwise, go to Step 8d.
  - d. If the subject prefers the plus axis coincident with the cylinder axis, increase the power of the cylinder by 0.25 diopter and return to Step 8b. Otherwise, proceed to Step 8e.

- e. When the subject feels that both positions are equally bad or good, and the cylinder power in the trial frame has changed by more than 0.50 diopter, return to Step 7c and re-check the axis if necessary. Otherwise, proceed to Step 9.

Note: If the cylinder is changed by more than 0.50 diopter, the **spherical equivalent** should be maintained. (For each 0.50 **plus** CX increase, add -0.25 to the sphere, for each 0.50 **minus** CX increase, add +0.25 to the sphere).

9. **Spherical Correction Refinement:** Recheck, or “**refine**” the power of the sphere by adding +0.25 and -0.25 spheres and changing the spherical power by 0.25 diopter increments of the appropriate sign until the subject cannot detect any improvement in vision. As a reminder, **minus sphere should only be added if the subject can read additional letters** and spherical testing should always begin and end with a plus lens.
10. Record the lens corrections obtained by subjective refraction for the right eye on the examination form in the section for visual acuity measurements as the correction obtained by protocol refraction for the right eye.
11. Repeat the entire process (Steps 1-10) for the left eye and record the refraction results on the VAE worksheet.

#### 21.4.3.1.6. Best Corrected Visual Acuity Measures

1. As a reminder, Charts 1, 2, and R (or 3) are used for testing the right eye, left eye, and refraction, respectively. Subjects should not see the charts until the test begins.
2. The lens correction from the subjective refraction should be in the trial frame worn by the subject.
3. **All eyes must be tested at 4 meters first, even if the refraction was performed at 1 meter.**
4. The subject should be seated comfortably directly in front of the chart so that the eyes remain at the 4 meter distance. Testing always begins with the right eye. The fellow eye should be occluded with a folded tissue or eye pad lightly taped over the eye behind the trial frame serves as an effective occlude that allows eccentric fixation without inadvertent use of the covered eye. After testing the right eye, occlusion of the right eye should be done BEFORE Chart 2 is put up for testing the left eye.
5. The subject is asked to read the letters slowly, approximately one letter per second. The subject should be told that only one chance is given to read each letter, but may change their mind before moving to the next letter. If the subject is unsure about the identity of the letter, then the subject should be encouraged to guess.
6. **The subject should begin by reading the top line of the chart and continue reading every letter on each smaller line, from left to right on each line. The subject should be encouraged to continue reading even if making mistakes. Each letter read is counted.** The examiner circles every correct letter read and totals each line and the whole column (0 if no letters are correct) on the data collection form. An X is put through letters read incorrectly. Letters, for which no guess was attempted, are not marked. When a subject reaches a level where he/she cannot guess, the examiner may stop the test

provided that the subject has made errors on previous guesses, which is a clear indication that the best visual acuity has been obtained.

7. **When a subject cannot read at least 20 letters on the chart at 4.0 meters, the subject is tested at 1.0 meter.** The distance from the subject to the chart should be measured again using the rigid one meter stick. **The distance is measured from the outer canthus to the center of the fourth letter (right eye) or the second letter (left eye) of the third line of the chart.** The spherical correction in the trial frame should be changed by **adding +0.75** to correct for the closer test distance. The subject may fixate eccentrically or turn or shake his/her head to improve visual acuity. Particular care should be taken to make sure the subject does not move forward when testing at 1 meter. The subject should be reminded to blink.
8. The examiner should not tell the subject if a letter was identified correctly. The subject may be encouraged by neutral comments, such as “good”, “next”, and “OK.”
9. The examiner should not stand close to the chart during testing. Attention should be focused on the subject and data collection form. If the subject has difficulty locating the next line to read, the examiner may go up to the chart and point briefly to the next line to be read, but then must move away from the chart.
10. **When 20 or more letters are read at 4 meters the visual acuity score for that eye is recorded as the number of letters correct at 4 meters plus 30.** The subject **gets credit for the thirty 1 meter letters** even though they did not have to read them. Otherwise, the visual acuity score is the number of letters read correctly at 1.0 meter plus the number, if any, read at 4 meters. If no letters are read correctly at either 4 meters or 1 meter, then the visual acuity score is recorded as 0.

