The charts used for measuring distance visual acuity must NOT be used for refraction. Refraction for each eye should be performed at **4 meters** unless the subject's visual acuity at 4 meters on the refraction charts (Chart R or Chart 3) is **worse than 20/160. If visual acuity is worse than 20/160 the eye is refracted at 1.0 meter.** If during the refraction process at 1 meter, the subject is reading letters on the eighth line or lower line of the chart, the refraction should be continue at 4 meters. Whenever a subject cannot read any letters on the top line of Chart R or Chart 3 at 1.0 meter the vision should be checked with a pinhole to see whether reduced vision is due, at least in part, to a larger refractive error. If there is no improvement with the pinhole, then the eye is exempt from refraction.

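### For eyes refracted at 1 m, the BCVA procedure leaves the trial lens nominally 0.75 D too plus at both the 4 m and the 1 m test

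*Protocol*

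**What the plan says.** The relevant steps are all in Protocol Appendix D.

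- **Where the eye is refracted** (21.4.3.1.4): "If visual acuity is worse than 20/160 the eye is refracted at 1.0 meter". The only route back is that if, during the 1 m refraction, "the subject is reading letters on the eighth line or lower line of the chart, the refraction should be continue at 4 meters". The refraction summary table agrees: 20/100 to 20/160 at 4 m, and 20/200 or worse at 1 m.
- **What goes in the frame** (21.4.3.1.6, item 2): "The lens correction from the subjective refraction should be in the trial frame worn by the subject".
- **Where testing starts** (item 3): "All eyes must be tested at 4 meters first, even if the refraction was performed at 1 meter".
- **When testing moves to 1 m** (item 7): "When a subject cannot read at least 20 letters on the chart at 4.0 meters, the subject is tested at 1.0 meter". For that test "The spherical correction in the trial frame should be changed by" adding +0.75, and the stated purpose is "to correct for the closer test distance".
- **Scoring** (item 10): an eye below 20 letters at 4 m scores its 1 m letters plus any 4 m letters, so readings at both distances count.

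Section 21.4.3.1.5.1 allows no other distances: "All refraction and vision testing must be done at 4 meters or 1 meter".

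**The concern.** Item 3 expressly foresees an eye refracted at 1 m and then tested at 4 m, but gives no lens conversion for it. Item 7 then adds plus power whatever the distance of the refraction. An eye refracted at 1 m would therefore be tested through the wrong lens twice. The error is excess plus, which accommodation cannot clear.

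BCVA is a listed safety parameter. SAP 8.3 tabulates study eyes that gain or lose at least 5, 10 or 15 letters at Month 12. Protocol 12.1.3 and SAP 4.4.1.2.1 treat a loss of 30 or more letters from baseline as sight-threatening. Protocol sections 8.1 and 8.2 set no lower limit on BCVA, so such eyes can enter. The lens error starts when an eye falls past 20/160 and stops when it recovers. In either direction part of the recorded change would then belong to the lens and not to the eye.

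**Working it through.** **Inputs.** Distances of 4 m and 1 m, also given as 157.5 and 39 3/8 inches (21.4.3.1.5.1). The add of +0.75 D (item 7). The 20/160 switch (21.4.3.1.4).

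**1. Reproduce the plan's figure.** The add for moving closer is the difference in vergence: 1/1 - 1/4 = 0.75 D. With the inch values it is 0.9999 - 0.2500 = 0.7499 D. The +0.75 D is correct if the frame holds a 4 m correction.

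**2. Follow the text for each refraction distance.** Let F be the far correction. The lens in focus at distance d is F + 1/d, so 4 m needs F + 0.25 and 1 m needs F + 1.00. Error is the lens in the frame minus the lens needed.

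| Refracted at | Frame at 4 m | Error at 4 m | Frame at 1 m, after the add | Error at 1 m |
|---|---|---|---|---|
| 4 m | F + 0.25 | 0.25 - 0.25 = 0.00 D | F + 1.00 | 1.00 - 1.00 = 0.00 D |
| 1 m | F + 1.00 | 1.00 - 0.25 = +0.75 D | F + 1.75 | 1.75 - 1.00 = +0.75 D |

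**3. Look for a step that removes it.** Sections 21.4.3.1.4 to 21.4.3.1.6 and the legible part of the summary table contain no instruction to take 0.75 D off a 1 m refraction, to waive the add, or to record the refraction distance.

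**4. Fix the scope.** Assume a 20/200 top line at 4 m, five letters a line and 0.1 log steps. This agrees with SAP Table 3: 85 letters less the 30 credited is 55 letters, or 11 lines, and line 11 is 200/10, or 20/20. Twenty letters at 4 m is then four lines, about 20/100. An eye at 20/125 to 20/160 is refracted at 4 m and also tested at 1 m, and row one of the table shows no error for it. Only eyes worse than 20/160 fall in row two.

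**5. Size in letters, as an illustration only.** Assume that 0.75 D of blur alone limits resolution to 1.5 to 3.5 arcmin. This figure is not in the documents. Take letters lost as 50 x log10(combined / unblurred), with an unblurred limit of 10 arcmin at 20/200 and 20 arcmin at 20/400.

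- 20/200, combined in quadrature: 50 x log10(10.11/10) = 0.2 to 50 x log10(10.59/10) = 1.3
- 20/200, added: 50 x log10(11.5/10) = 3.0 to 50 x log10(13.5/10) = 6.5
- 20/400, in quadrature: 0.1 to 0.3
- 20/400, added: 50 x log10(21.5/20) = 1.6 to 50 x log10(23.5/20) = 3.5

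The range is too wide to serve as an estimate. It does show the loss shrinking as acuity worsens.

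**6. Test the fix.** Subtract 0.75 D before the 4 m test: 1.00 - 0.75 - 0.25 = 0.00 D. Add it back for the 1 m test: 0.25 + 0.75 - 1.00 = 0.00 D. Eyes refracted at 4 m are unchanged.

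**The case against.** The strongest reply is that this is an omitted condition and not a wrong number, and that it hardly matters in practice.

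- **Intent and training.** Item 7's stated purpose presumes a 4 m correction in the frame. Testing is limited to trained examiners, results go on a sponsor worksheet that is not in the documents, and the sponsor supplies instructional material (Protocol 16.1). The summary table is also broken in the text available, so a note missing from it is weak evidence. All this stands, and some sites may have converted unprompted. But the written steps do not say so, and conversion at some sites only would add inconsistency.
- **Coarse steps.** At 20/200 to 20/400 the sphere moves in 2.00 D steps with 1.00 D refinement. Below 20/400 there is no refinement. So 0.75 D is a nominal offset and not the defocus of each eye. This stands too, but the offset has one direction, and the push-plus rule gives no reason to expect rounding to remove it.
- **Narrow effect.** The study is single-arm and descriptive, the letter-change tables cover study eyes only, and an eye refracted at 1 m at both visits carries the offset twice. This also stands.

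A reader might infer that all low-vision eyes are tested out of focus. The documents do not support that, because eyes refracted at 4 m get the right lens at both distances even when they need the 1 m test. A reader might also infer that the error by itself moves eyes across the 5-letter line. In the illustration above that happens only near 20/200, with the additive model and the upper part of an assumed range. Losses worked out at exactly 20/160 would be beside the point, since that eye is refracted at 4 m.

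**Conclusion.** The point holds for eyes refracted at 1 m, that is, eyes worse than 20/160. Followed literally, the procedure leaves their lens nominally 0.75 D too plus at 4 m and at 1 m. The figure of +0.75 D is right, but applying it without condition is not.

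The effect on BCVA in letters, and the number of eyes affected, cannot be derived from the documents. Bias in change from baseline mainly concerns eyes that cross 20/160 between visits: a loss is overstated for an eye that falls past it, and a gain for one that recovers. With the 60 subjects in SAP 3.3, one misclassified study eye is 1/60, or 1.7%.

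The conclusion assumes that examiners follow the text without converting. The cancellation assumes that both visits used the same procedure. For subjects who left SAKURA on Day 1, baseline BCVA comes from the SAKURA termination visit (Protocol 7.5.1), whose procedure is not in these documents. Nothing here shows that BCVA results are unreliable overall. This is a correction that should be made to a measurement procedure.

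**What to change.** In section 21.4.3.1.6:

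- **Item 3:** if the refraction was done at 1 m, subtract 0.75 D of sphere before the 4 m test.
- **Item 7:** add +0.75 D only to a 4 m or 4 m-equivalent correction, so that the 1 m test uses a 1 m refraction unchanged.
- **Worksheet:** record the refraction distance, if it is not already recorded.

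No conversion is needed for the next visit's starting lens. That value is only approximate and is refined subjectively.

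The cost is two conditional sentences and at most one worksheet field, with no added procedure. SAP 3.3 says enrolment is complete, so for data already collected the sponsor can ask sites which eyes were refracted at 1 m, and whether the lens was converted, and flag those eyes in the BCVA listings.

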#### **21.4.3.1.7. Testing for Count Finger Vision, Hand Motion Vision and Light Perception/No Light Perception Vision**

If the subject's visual acuity is so poor that he/she cannot read any chart letters when tested at one meter then the subject's ability to count fingers, detect hand motion, or have light perception should be evaluated.

##### **21.4.3.1.7.1. Testing for Count Fingers Vision**

In testing for count fingers vision, the examiner's hand holding 1, 2, or 5 fingers is held steady at a distance of two feet directly in front of the eye being examined. The fellow eye is completely occluded with a patch on the face. A light should be shone directly on the hand from behind the subject. The examiner's fingers should be presented in random order and repeated five times. Eccentric fixation, if present, should be encouraged. If the subject correctly identifies three of the five presentations, then count fingers vision is noted. If not, then the subject must be tested for hand motion vision.

##### **21.4.3.1.7.2. Testing for Hand Motion Vision**

The examiner's hand with all fingers spread out should be extended two feet directly in front of the eye being examined. The fellow eye should be occluded with a patch on the subject's face. A light should be shown directly on the examiner's hand from behind the subject. The examiner's

hand should be moved in an up-and-down direction (vertically) or in a side-to-side direction (horizontally) at a constant speed of approximately one back and forth presentation per second. The subject is instructed that the examiner's hand will be presented and they will have to respond to the question: "What am I doing with my hand?" This should be repeated five times. Three out of five correct responses indicate that hand motion vision is present. If the subject does not correctly identify three of five presentations, then you must test for light perception.

#### **21.4.3.1.7.3. Testing for Light Perception/No Light Perception Vision**

Light perception should be tested with an indirect ophthalmoscope in a darkened room. The fellow eye should be completely patched and covered by the subject's hand. The indirect ophthalmoscope light should be in focus at 1 meter with the rheostat set at maximum voltage. From that distance the beam should be directed in and out of the subject's eye at least four times, and the subject should be asked to respond when he/she sees the light. If the examiner is convinced that the subject perceives the light, vision should be recorded as "light perception," if not, vision should be recorded as "no light perception."

4M Refraction Protocol Summary							
Refraction Distance	Check Sphere First then Power			Check Cylinder Axis		Sphere "Refinement"	
	Power (a)	Increment	Axis (b)	Power (c)	Increment	Power (d)	Increment
20/10 – 20/80 (4 meters)	+.50 -.50	+.50 -.50	.25 JCC	.25 JCC	+.25 -.25	+.25 -.25	+.25 -.25
20/100 – 20/160 (4 meters)	+1.00 -1.00	+1.00 -1.00	.50 JCC	.50 JCC	+.50 -.50	+.50 -.50	+.50 -.50
20/200 – 20/400 (1 meter)	+2.00 -2.00	+2.00 -2.00	1.00 JCC	1.00 JCC	+1.00 -1.00	+1.00 -1.00	+1.00 -1.00
<20/400 (1.0 meters) sequence refraction a-d	+2.00 -2.00	+2.00 -2.00	No cylinder test required			No refinement required	

